## Research Design and Methods

The proposed study is a pilot RCT with multi-method longitudinal assessment (refer to **Figure 1** for an overview of study activities). The study has three primary aims: (1) to assess the feasibility of recruiting Veterans of color into an RCT of RBSTE, (2) to understand Veterans' views of the acceptability and appropriateness of intervention content and provider behavior and the feasibility of participation in a future RCT; and (3) to refine a holistic assessment strategy.

**Figure 1.** Schematic of study activities

Veterans who express interest in study participation will be contacted by study staff and provided with general information about the study. Those who continue to be interested will engage in the informed consent process in person or using remote procedures (e.g., VA Docusign), depending on personal and health considerations. Veterans who provide written consent will go on to complete the baseline assessment (refer to **Assessment approach**). Randomization will occur at the group level: once a cohort of 4-10 Veterans has enrolled and completed the baseline assessment, the cohort will be randomized by the study statistician. Although group randomization has disadvantages as compared to individual randomization (e.g., dependence among group members, lack of blinding of the final 1-2 groups), these can be managed and are outweighed in our experience by facilitating recruitment because groups can begin more quickly. Groups will meet in **weekly 90-minute sessions for 8 weeks**. Videoconferencing will be used to minimize barriers to participation, including transportation and public health concerns. The assessment battery will be repeated at the end of the group. Participants will be compensated \$50 for each assessment point for total compensation of \$100.

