**Assessment approach.** Because of the history of human rights violations and misconduct in medical and psychological research, many people of color mistrust research activities (Suite, La Bril, Prim, & Harrison-[name], 2007). This is an important reason to study the feasibility of the proposed data collection strategy and motivation to prioritize brevity of our assessment battery. A record of study participation will be gathered following CONSORT guidelines to quantify enrollment and retention. Assessments will be completed within 1 month prior to the beginning of group and within 1 month after the end of group. The sample will be characterized at the baseline assessment. Participant characteristics including age, gender, race/ethnicity, education, work status and financial and housing stability, will be gathered using a demographic questionnaire. Adherence to group will be quantified based on attendance at sessions and proportion of homework completed (**coded as none/partial/complete as judged by the therapist**).

**Recruitment feasibility.** Aim 1 of this study involves evaluating strategies for recruiting VOC for this type of study. *Enrollment rate*, defined as the number of contacts per enrollment, will be used to optimize the future approach to accrual. There is no target enrollment rate as many can be acceptable; this metric will serve to guide resource allocation. **Gathering information from Veterans and providers about reasons for declining participation or referral, however, will be important in determining the representativeness of the sample.** *Number of enrollments per month* will be viewed as successful if at least four individuals are enrolled per month as that level of recruitment represents a reasonable period (average 2-3 weeks) for a Veteran to wait for a group to begin. *Initiation rate* will be defined as the proportion of Veterans who initiate the intervention among all consented participants. This will inform recruitment strategies (i.e., which strategies lead to the highest proportion of treatment initiation) but also may help to identify areas of improvement in terms of connecting Veterans to the project. As these behaviors are recorded prior to the first session, we do not expect group differences.

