**Acceptability, appropriateness and feasibility.** Relevant to aim 2, participant behavior is one important marker of participants' perceptions of the project and their ability to comply with research procedures. *Retention rate* will be defined as the percent of enrolled sample completing all assessment time points; at least 80% completion will be considered successful. *Per protocol completion rate* will be defined as the proportion of subjects who complete 6 or more sessions among those who initiate treatment; at least 90% completion will be considered successful. *Intent-to-treat completion rate* will be defined as the proportion of subjects who complete 6 or more sessions of intervention among all randomized subjects; at least 80% is the target. *Compliance with homework* will be assessed with a goal of at least 80% moderately or fully complete (refer to **Assessment approach**). In addition, Veterans will be directly queried about their experience using the *Acceptability of Intervention Measure (AIM)*, *Intervention Appropriateness Measure (IAM)*, and *Feasibility of Intervention Measure (FIM)*. The 5-item measures have strong content validity, test-retest reliability and sensitivity to change (Weiner et al., 2017). The psychotherapy version of the *Provider Rating Scales*, which were previously used to assess perceptions of VA mental health providers (Spoont et al., 2017), will be used to assess Veterans' perceptions of the group leader. Between-group differences on these measures would likely reflect the difference in content between the two groups.

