We will assess four outcome measures for enrollment and retention: 1) *enrollment rate* defined as the proportion of consented subjects among all screened and eligible patients; 2) *initiation rate* defined as the proportion of subjects who initiate the intervention among all consented subjects; 3) *per protocol completion rate* defined as the proportion of subjects who complete 5 or 6 sessions of intervention among those who start the intervention; 4) *intent-to-treat completion rate* defined as the proportion of subjects who complete 5 or 6 sessions of intervention among all randomized subjects. The 95% CI (based on normal approximation or exact binomial test when appropriate) will be estimated for all these rates for overall and by each intervention group. The rates for the RBSTE and PCT groups will be compared by Fisher's exact test. Multivariable analysis will be also performed to examine the difference in outcomes between intervention groups using logistic regression.

**Aim 2:** *To understand Veterans' views of the acceptability and appropriateness of treatment content, the feasibility of participation, and perceptions of provider behavior and attitudes.*

The AIM, IAM, FIM and Provider Rating Scales will be estimated by mean, SD and 95% CI. Intervention groups will be compared by Wilcoxon rank sum test. Multivariable analysis will be also performed to examine the difference in outcomes between intervention groups using linear regression.

**Aim 3:** *To optimize the strategy for holistic evaluation of intervention effects.*

As aforementioned, we will include a comprehensive list of cardiometabolic, neuroendocrine, and inflammatory markers that had been shown as reliable markers of AL in the literature to derive an AL index for each participant. We hypothesize that AL index at baseline will be associated with perceived discrimination as well as other psychosocial outcomes and that pre to post-intervention changes of AL index will differ between the two groups. We will perform regression analysis and variable selection using LASSO (Tibshirani 1996) to identify a smaller subset of the AL markers at baseline that show significant associations with psychosocial outcome measures. The effect size for pre and post change in AL markers will be estimated. This will inform future efficacy and effectiveness studies in potential reduction of a list of biomarkers to enhance feasibility, efficiency and reduce participant burden.

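### Initiation follows randomization, so the plan's reason for expecting no arm difference does not cover it, and the starter-only comparison of completion should be descriptive

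*Combined protocol and SAP*

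**What the plan says.** All references are to the combined protocol and SAP, Research Design and Methods.

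- Design overview: "Randomization will occur at the group level", and "once a cohort of 4-10 Veterans has enrolled and completed the baseline assessment, the cohort will be randomized by the study statistician". Sessions come after that.
- Recruitment feasibility: three metrics are described, namely enrollment rate, enrollments per month and initiation rate. Initiation is "the proportion of Veterans who initiate the intervention among all consented participants". The paragraph closes: "As these behaviors are recorded prior to the first session, we do not expect group differences".
- Acceptability, appropriateness and feasibility: per-protocol completion is "the proportion of subjects who complete 6 or more sessions among those who initiate treatment; at least 90% completion will be considered successful". Intent-to-treat completion uses all randomized Veterans as its denominator, with a target of at least 80%.
- Analyses, Aim 1: enrollment, initiation, per-protocol completion and intent-to-treat completion are each estimated overall and by arm. Then: "The rates for the RBSTE and PCT groups will be compared by" Fisher's exact test, with logistic regression as the multivariable analysis.

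**The concern.** What justifies expecting no arm difference is that an event precedes allocation. Preceding the first session is not enough. Enrollment meets that condition and initiation does not, because a Veteran starts or fails to start after the cohort has been assigned.

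An arm difference in starting is plausible on the plan's own description. Recruits must report discrimination and stress, and PCT carries no race-specific content. RBSTE also already runs in three clinics at the same site. Whether Veterans learn their arm before the first session is not stated.

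If starting does depend on arm, the starters in the two arms are differently selected. Comparing their completion rates is then no longer a randomized comparison. A reader of the pilot could take a higher starter-only rate in one arm as better tolerability when that arm simply lost its less committed members before the first session.

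**Working it through.** **1. Order of events.** Consent, then baseline assessment, then randomization of the cohort, then sessions. Enrollment rate and enrollments per month are settled before randomization. Initiation, per-protocol completion and intent-to-treat completion come after it.

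**2. The plan's own figure for initiation.** The Sample size section gives 95% interval widths of 0.222 (n = 48) and 0.308 (n = 24) at an initiation rate of 0.80. The Wilson width is 2z·√(p(1−p)/n + z²/(4n²)) / (1 + z²/n), with z = 1.96:

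- n = 48: 2 × 1.96 × √(0.003333 + 0.000417) / 1.0800 = 0.222
- n = 24: 2 × 1.96 × √(0.006667 + 0.001667) / 1.1601 = 0.308

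Both figures reproduce. (The text calls the interval exact binomial, which would give 0.242 and 0.346. That is a separate labelling matter.) Initiation within an arm will be known only to about ±15 percentage points.

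**3. How the two completion rates relate.** Let R be randomized, S starters and C completers in an arm. Then C/R = (S/R) × (C/S): intent-to-treat completion equals the share starting times per-protocol completion. If the share starting is the same in both arms, the two comparisons must agree in direction. Where arm B has the higher per-protocol rate, they disagree when (S/R in A) ÷ (S/R in B) exceeds (C/S in B) ÷ (C/S in A).

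**4. Illustration.** The documents give no arm-specific rates, so these counts are assumed, at the planned 24 per arm.

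| | Arm A | Arm B | Fisher p |
|---|---|---|---|
| Start / randomized | 24/24 = 100% | 20/24 = 83.3% | 0.109 |
| Complete / starters | 21/24 = 87.5% | 18/20 = 90.0% | 1.000 |
| Complete / randomized | 21/24 = 87.5% | 18/24 = 75.0% | 0.461 |

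The condition in step 3 is met: 1.000/0.833 = 1.20, and 0.900/0.875 = 1.03. Among starters B looks better and only B reaches 90%. Among all randomized A is better and only A reaches 80%.

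**5. Range.** Assume everyone starts in A and a share s starts in B. Completion is 95% in those who would start in either arm, and r in those who would start only in A. Then per-protocol completion is 0.95s + (1−s)r in A and 0.95 in B. Intent-to-treat completion is 0.95s + (1−s)r in A and 0.95s in B.

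| s | A, both rates (r = 50% to 70%) | B, starters | B, randomized |
|---|---|---|---|
| 0.95 | 92.75% to 93.75% | 95.0% | 90.25% |
| 0.90 | 90.5% to 92.5% | 95.0% | 85.5% |
| 0.80 | 86.0% to 90.0% | 95.0% | 76.0% |

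Under this model the directions differ whenever r lies between 0 and 95%. The model builds in both necessary ingredients: starting that depends on arm, and extra starters who are less likely to complete.

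**6. Could a test of initiation clear the assumption?** With 24 per arm at two-sided 0.05, exact Fisher power is 24% for initiation of 95% versus 80%, and 40% for 95% versus 75%, before any loss from group randomization. A nonsignificant result would say little.

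**The case against.** The strongest reply is that the safe analyses are already in the plan. Aim 1 estimates and compares both initiation and intent-to-treat completion by arm, so a difference in starting would be reported and any reversal would be visible beside the intent-to-treat result. The primary analysis is overall and within arm, and the study disclaims efficacy testing. All of this stands, and it limits the harm to the starter-only comparison and the one sentence.

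It is also fair that the documents do not show Veterans know their arm. The design overview lists "lack of blinding of the final 1-2 groups" as a drawback. That may imply some blinding of earlier groups, though it does not say of whom. Consent pages are not in the public text, so silence here is not evidence of disclosure.

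Stronger readings that a reader might infer, and that the documents do not support:

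- *The plan tells readers to discount an arm difference in starting.* It states an expectation, then tests initiation by arm anyway.
- *Refusal of PCT is a demonstrated threat.* No arm-specific starting rates or refusal data are given.
- *The two success levels conflict, because 0.80 × 0.90 = 0.72 falls below the 80% target.* The 0.80 only illustrates interval width. The next illustration is 0.90, and 0.90 × 0.90 = 0.81 meets the target. The product also multiplies a rate among consented Veterans by one among starters, so it equals intent-to-treat completion only if every consented Veteran is randomized.

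What remains is that the stated rationale is wrong for initiation, and that one planned between-arm test lacks the protection of randomization.

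**Conclusion.** The point holds as a modest, inexpensive improvement. The sentence in Recruitment feasibility is right for the two enrollment metrics and wrong for initiation. The between-arm test of per-protocol completion conditions on an event after randomization and can point the other way from the intent-to-treat comparison. In the illustration the difference, A minus B, is −2.5 percentage points among starters and +12.5 among all randomized.

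A reversal needs starting to depend on arm, whether systematically or by chance with only four groups per arm, and starters to differ between arms in their tendency to complete. The documents establish neither. The counts are assumed, and neither completion contrast would be significant at this size. It would be wrong to infer that the pilot's conclusions will be reversed, since the intent-to-treat comparison is already planned.

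A related gap is the denominator of initiation. Consented Veterans who are never randomized have no arm, so a by-arm initiation rate among all consented is not properly defined.

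**What to change.** 1. In Recruitment feasibility, limit the sentence about expecting no group differences to enrollment rate and enrollments per month.
2. For the arm comparison, compute initiation among randomized Veterans. The rate among all consented can stay as an overall figure.
3. In Analyses, Aim 1, make intent-to-treat completion the between-arm comparison of completion, for both Fisher's exact test and logistic regression. Report per-protocol completion descriptively, overall and within arm, with its interval.
4. State when participants learn their arm.

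The cost is wording and one fewer low-power between-arm test. Attendance is already recorded, so no new data are needed. Separately, the session count that defines completion differs between the Acceptability paragraph (6 or more) and Aim 1 (5 or 6). The two should be reconciled, but this point does not depend on which is used.

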RBSTE has been applied clinically in multiple facilities. To date, enrollees have been largely Black and male (Carlson et al., 2018). Qualitative evidence from these initial applications suggests its promise. Specifically, Veterans expressed appreciation for the information provided during the group, camaraderie among group members and the freedom to discuss experiences of racism. In their view, the group helped them to develop greater self-efficacy for managing racism as well as better coping and emotion regulation (Carlson et al., 2018). An adaptation of RBSTE was applied for Black women at risk of cardiovascular disease (CVD;  $n = 22$ ; Conway-Phillips et al., 2020). On average, these women felt that the program was very helpful for management of chronic stress (8 on a scale of 0-10). Ninety-five percent said that they would recommend the program to a friend, and 81% were actively applying the skills they had learned. Further, the women reported that the group increased their awareness of and coping with race-related stressors and increased both emotion regulation and a sense of empowerment. A preliminary RCT of the adaptation as compared to a no-intervention control condition ( $n = 74$ ) less avoidant coping in the experimental group but no differences from control in terms of depression, stress, anxiety or inflammatory markers, although small reductions in both inflammatory marker levels tumor necrosis factor alpha (TNFa) and high sensitivity C-reactive Protein (hsCRP) were detected (Saban et al., 2021). It is possible that the very low baseline levels of emotional distress in this group that was recruited based on medical factors, as opposed to stress related to experiences of discrimination, may be creating a floor effect that is potentially obscuring change in mental health outcomes. In addition to enrolling BIPOC veterans who report a defined level of experienced discrimination and stress (see inclusion criteria), we believe that our approach to assess its biological impact in a more comprehensive and integrated manner using an AL index calculated from ten biomarkers would lead to a rigorous investigation of biological impact of both race-based trauma/stress and the RBSTE intervention. We anticipate that AL would demonstrate high sensitivity in detecting such impacts/effects beyond that of a single biomarker.

[figure not shown]

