**Allostatic load** will be assessed pre and post intervention by measuring 10 markers of interest, specifically hemoglobin (Hb) A1c, systolic and diastolic blood pressure (SBP, DBP), high density lipoprotein (HDL), triglycerides, urine epinephrine (Epi) and norepinephrine (NE), waking salivary cortisol, interleukin (IL)-6, and hsCRP. **Venous blood will be drawn via vena puncture between 8-10 AM after overnight fasting and sent to the VA clinical chemistry lab to measure Hb A1c and the lipid panel (for HDL and triglycerides). Plasma from 5mL of blood will be collected and frozen at -80 C until assayed to measure IL-6 and hsCRP using electrochemiluminescence assay (Mesoscale Discovery). Spot urine will be collected for Epi and NE and frozen at -80 C until assayed using ELISA-based immunoassay and adjusted for creatinine levels, which are well representative of general sympathetic output of an individual. Salivary cortisol levels will be measured in saliva collected the morning of the blood draw visit upon wakening. Saliva samples will be frozen at -80 C until assayed using immunoassay (Salimetrics). Both pre and post samples from a given participant will be assayed together using reagents from a single lot number by one technician who is blinded to the condition. All biomarker assays will be done in [name] lab where they are routinely performed, and the intra- and inter-assay CV's of these proposed markers are <10%. Seated SBP and DBP will be measured after a 5-min of rest, and the average from 3 readings will be used. The AL index for each participant will be calculated by assigning 1 to the highest quartile values vs. the rest 0 for each marker and summing them (Rosemberg, Granner, Li & Seng, 2020).** Thus, a possible range of 0 to 10 would emerge, indicating the lowest to highest AL across the participants. We acknowledge that there have been differing ways for AL index calculation as well as included markers. Our proposed methods and the markers are based on the best consensus from a number of studies and reviews that also demonstrated evidence of AL reflecting chronic stress and eventual health outcomes including all-cause mortality (Duong et al., 2017; Guidi, Lucente, Sonino, & Fava, 2021; Juster, McEwen & Lupien, 2010).

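### The allostatic load rule gives the load point for HDL to the highest (favourable) quartile, so the 0–10 sum does not run from lowest to highest load as the plan says

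*Combined protocol and SAP*

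**What the plan says.** The Allostatic load paragraph of Research Design and Methods says that AL "will be assessed pre and post intervention by measuring 10 markers of interest". The list of ten includes "systolic and diastolic blood pressure (SBP, DBP), high density lipoprotein (HDL), triglycerides". A single scoring rule covers the whole list: "The AL index for each participant will be calculated by assigning 1 to the highest quartile values vs. the rest 0 for each marker". The points are then summed, and the resulting 0 to 10 range is described as "indicating the lowest to highest AL across the participants". Background and Significance presents AL as a measure of bodily wear from chronic stress that goes with more disease and death, so a higher score is meant to be worse.

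The index has two stated uses, both under Aim 3 in Analyses. The first is cross-sectional: "We hypothesize that AL index at baseline will be associated with perceived discrimination as well as other psychosocial outcomes". The second is that "pre to post-intervention changes of AL index will differ between the two groups". Preliminary Studies sets the expectation for it: "We anticipate that AL would demonstrate high sensitivity in detecting such impacts/effects beyond that of a single biomarker".

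The document gives no exception for HDL, no direction of risk for any marker, and no statement of which sample or visit supplies the quartile cut points.

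**The concern.** For nine of the ten markers the highest quartile is the adverse one. For HDL the adverse end is low, so a uniform highest-quartile rule awards the load point to the participants with the most favourable HDL and withholds it from those with the least favourable. The rule and the plan's own reading of the sum cannot both hold.

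An analyst coding from this text would build an index in which one component works against the other nine. That would weaken both index hypotheses. It would also be hard to notice: a quartile indicator averages 0.25 whichever end is scored, so the index mean is 10 × 0.25 = 2.5 either way.

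There is a secondary gap. AL is measured before and after the intervention, and the scoring of change depends on whether cut points are fixed or re-derived at each visit. The plan does not say which.

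**Working it through.** **Inputs.** From the document: ten markers including HDL; one point for the highest quartile of each; planned n about 48 (24 per arm), possible range 24–60. From general clinical knowledge: high HDL is favourable. The document gives no inter-marker correlations, pre-post correlations or expected shifts, so those below are assumptions, shown as ranges where they matter.

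**The plan's own range.** Ten 0/1 items sum to between 0 and 10, so the arithmetic range reproduces. Its meaning does not:

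| Profile | HDL scored as written | HDL scored on lowest quartile |
|---|---|---|
| Adverse quartile on all ten | 9 + 0 = 9 | 9 + 1 = 10 |
| Favourable quartile on all ten | 0 + 1 = 1 | 0 + 0 = 0 |

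A score of 10 under the written rule requires a favourable HDL.

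**How many participants are mis-scored (no ties).** The top HDL quartile gets 1 instead of 0 and the bottom quartile 0 instead of 1; the middle half is unaffected. That is 25% + 25% of the sample: 12 + 12 at n = 48, 6 + 6 at n = 24, 15 + 15 at n = 60.

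**Baseline hypothesis.** One-factor normal model, equal inter-marker correlation r, n = 48, 3,000 samples per setting. Entries are the correlation of the index with underlying burden when HDL loads like the other markers:

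| r | HDL scored correctly | HDL as written |
|---|---|---|
| 0.1 | 0.59 | 0.51 |
| 0.2 | 0.72 | 0.64 |
| 0.3 | 0.79 | 0.72 |
| 0.4 | 0.83 | 0.76 |

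The loss is 0.065 to 0.085. It is 0.03 to 0.04 if HDL loads half as strongly, and about 0 if HDL is unrelated to burden. With equal loading, leaving HDL out altogether (0.58, 0.71, 0.78 and 0.82 at the same values of r) does better than scoring it as written.

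**Between-arm hypothesis.** Suppose one arm improves by d standard deviations on every marker, with cut point z = 0.674 (the 75th percentile). A correctly scored marker changes by P(Z > z + d) − 0.25. HDL as written changes by P(Z > z − d) − 0.25, which is a rise.

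| d | Correct marker | HDL as written | Ten correct | Nine correct + HDL as written | Shrinkage |
|---|---|---|---|---|---|
| 0.1 | −0.0307 | +0.0328 | −0.31 | 9 × (−0.0307) + 0.0328 = −0.24 | 21% |
| 0.2 | −0.0591 | +0.0676 | −0.59 | 9 × (−0.0591) + 0.0676 = −0.46 | 21% |
| 0.3 | −0.0851 | +0.1040 | −0.85 | 9 × (−0.0851) + 0.1040 = −0.66 | 22% |

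If HDL does not move, nothing is lost.

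**Cut-point gap.** Simulated with all markers correctly scored, n = 48, one arm improving by 0.2 SD, the other unchanged, and pre-post correlation 0.6. Results barely vary over r = 0.1 to 0.4:

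| Cut points from | Improving arm | Unchanged arm |
|---|---|---|
| Each visit separately | −0.32 | +0.32 |
| Baseline, applied to both visits | −0.53 | +0.08 |
| Both visits pooled | −0.62 | 0.00 |

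Visit-specific cut points hold the proportion above the cut at about a quarter every time, so the overall change is close to zero by construction and the unchanged arm appears to worsen. The arm contrast is nearly the same in all three (−0.61 to −0.64).

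**The case against.** The best defence is that the wording is shorthand. The plan attributes the rule to a published method, acknowledges that AL indices are computed in different ways, and states the intended direction in the very next sentence. The cited method may reverse HDL, and the team may intend to. That is possible, but the text says highest values for each marker, not highest risk, and a plan should be codable as written. If reversal is intended, the correction simply records it. The harm described here therefore arises if the rule is applied literally.

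The size can also be challenged, and part of this stands. The index is weakened, not inverted: the literal and corrected versions correlate at about 0.91 to 0.97. The 21–22% is in raw index points. Reversing one correlated marker also narrows the spread of change scores, so the standardised arm difference falls by less, about 12–18% for a 0.2 SD shift with pre-post correlation 0.6. The absolute loss in that case is about 0.13 points, against a standard error of roughly 0.5 to 0.7 with 24 per arm, ignoring clustering.

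It is also fair that this is a feasibility pilot not powered for hypothesis tests, that no feasibility target depends on the index, and that it can be rescored from raw values. This limits the consequence but does not reconcile the rule with its stated meaning.

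On cut points, the objection that neither named index hypothesis is much affected is right. The gap matters for index change reported within each arm or overall, the way Analyses says the primary analysis will be run.

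**Conclusion.** The concern holds. As written, the rule scores HDL in the wrong direction and contradicts the plan's own description of the 0–10 range; the only outside premise is that high HDL is favourable.

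Half the sample is off by one point. The effect on the two index hypotheses runs from nil, when HDL carries no information or does not move, to the modest losses shown above when it behaves like the other nine markers. These sizes rest on a normal one-factor model and on assumed correlations and shifts, not on figures in the plan.

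The damage is limited to the exploratory AL index. Feasibility outcomes, sample size and the effect sizes for individual markers do not use it. Nor does the LASSO on individual markers, although the plan does not say whether markers enter it as measured values or as 0/1 codes; with 0/1 codes the HDL item would carry the same reversal. The unnamed cut-point reference is a secondary omission and would not justify a finding alone.

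**What to change.** Reword the scoring rule in the Allostatic load paragraph along these lines: *assign 1 to the highest-risk quartile (the lowest quartile for HDL, the highest quartile for the other nine markers) and 0 otherwise, then sum.*

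Add one sentence naming a single set of cut points for both visits, for example: *quartile cut points are taken from the baseline sample with both arms pooled and applied unchanged to post-intervention values.* Another common reference, such as both visits pooled, is equally defensible if named in advance.

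The cost is two sentences, with no new assays, visits or data. Raw values could be rescored later, but settling direction and cut points before results are seen avoids a post hoc scoring choice and keeps a mis-scored index from informing the future trial.
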